6.2.4 Follow-up Visits

Day 7 (+/- 2 days) Assessments/Activities:

- At-home online assessments:
 - PHQ-9
 - Inventory of Statements About Self-Injury, since last visit (ISAS-SLV)
 - Side Effect Checklist

- Ongoing Medication Uses and Changes: Subsequent Visits

Visit 3 (Day 14 +/- 2 days) Assessments/Activities:

- In-person or video conference assessments:
 - PHQ-9
 - ISAS-SLV
 - Side Effect Checklist
 - Ongoing Medication Uses and Changes: Subsequent Visits
- Capsules count previous dispensed amount, check medication tracking table or REDCap survey records (participant counts pills over zoom during 14-day visit if it is conducted virtually)

Day 21 (+/- 2 days) Assessments/Activities:

- At-home online assessments:
 - PHQ-9
 - Inventory of Statements About Self-Injury, since last visit (ISAS-SLV)
 - Side Effect Checklist
 - Ongoing Medication Uses and Changes: Subsequent Visits

6.2.5 Completion/Final Evaluation

In the context of the global pandemic, we have shortened the final visit to reduce the time that participants will be required to be indoors in the CMRR. Thus, during the pandemic, we will utilize an abbreviated protocol (3 hours instead of 8, with fewer blood draws.) The PI will determine if and when to resume the original PK sample collection scheme (longer protocol) for visit 4 once it is safe to do so based on the status of the global pandemic and the guidance from the University.

Visit 4 (Day 28-32 days) Assessment/Activities per abbreviated PK sample collection scheme:

- COVID screen
- MRI Safety Screen
- Urine Toxicology Screen
- Pregnancy Test
- IV catheter placement or a series of needle stick(s) if the participant prefers
- 3-5 blood collections
- Neuroimaging procedure (MRI brain scan)
- PHQ-9

- BDI-II
- BSS
- ABUSI
- ISAS-SLV
- DSHQ-M
- Cash Choice Task
- Side Effect Checklist
- Ongoing Medication Uses and Changes: Subsequent Visits

Participants will return to the CMRR for a 3-8 hour visit ~4-weeks after beginning study drug, on Day 28 - 32 and present their remaining medications for capsule count to assess drug compliance. This visit will entail a repeat of the baseline neuroimaging procedure and multiple blood collections for PK analysis. The participant will be asked if they would prefer placement of IV catheter versus a series of needle sticks every time a blood sample is collected. We will collect an initial blood sample to measure trough NAC and CYS levels, as well as oxidative stress measurements detailed below. Then, participants will take their final oral dose. We will collect additional blood samples (2-5) starting at 15 minutes and ending at ~120-300 minutes following the final oral dose to measure NAC and CYS levels (abbreviated COVID-19 protocol: just 2 post-NAC dose blood draws, one right before and one right after the MRI scan). Neuroimaging will begin ~15 minutes after the final dose and will last ~60-90 minutes. Following this MRI scan, participants will be interviewed to ascertain medication side effects using a checklist. Although this study is not designed to examine clinical effects, to allow for exploratory analyses examining links between concurrent symptoms and biology, we will ask participants to complete the ABUSI, an abbreviated form of the SITBI (modified to query the NSSI thoughts, urges and behaviors since the prior clinical assessment), the ISAS-SLV to assess NSSI episodes, BDI-II, PHQ-9 and BSSI to assess depression symptoms and current suicidal thoughts and behaviors, the DSHQ-M to assess mood in relationship to NSSI episodes, and the one-question Cash Choice Task as a delay discounting measure (Wulfert et al., 2002) . The PHQ-9, ISAS-SLV, ABUSI, DTS, Cash Choice Task, Side Effect Checklist, and Ongoing Medication Uses and Changes: Subsequent Visits will be available online via REDCap. Paper versions will be available if necessary (REDCap down, computer unavailable, etc.) Participants who are unable to complete all online self-report questionnaires in-person due to time constraints will be emailed an access code for each questionnaire and a link to the REDCap website. Upon opening the website link, they will be prompted to enter their access code in order to fill out questionnaires. Upon administration of the final dose of study drug, participants will be instructed to inform study staff of any potential adverse effects that occur after leaving the research facility. In addition, 24-72 hours after the final dose of NAC, participants will receive a phone call from study staff to assess any potential adverse effects after the final dose of study drug and address any lingering questions/concerns about study participation and/or referral suggestions for future

clinical care addressing NSSI or psychiatric symptoms/co-morbidities. If the participant unexpectedly needs to have their final visit rescheduled, we will prescribe an additional small supply of study medication to allow the participant to continue taking study medication up until the final visit, to a maximum of 35 days.

Payment

Participants will be compensated directly using the Greenphire ClinCard. Each task completed will have attached a specific compensation amount. Once the task is completed research staff will load the amount attached to that task on to the participants Greenphire ClinCard. In cases where a participant only completed a portion of a visit, a portion of the compensation would be provided depending on what was completed. If any visit or part of the visit needs to be repeated for reasons beyond participants' control, they would be compensated.

- 1) Day 0 (in-person or through video conferencing) (visit 1): Initial clinical assessment: \$40
- 2) Day 1 (in-person visit 2): Baseline assessments, MRI scan and blood draw: \$50
- 3) Day 7 (at home): Online questionnaires: \$10
- 4) Day 14 (in-person or through video conferencing) (visit 3): Mid-study visit questionnaires: \$10
- 5) Day 21 (at home): Online questionnaires: \$10
- 6) Day 28 - 32 (in-person visit 4): Post-dose MRI and blood samples (over 3-4hours per abbreviated PK sample collection plan or 6-8 hrs): \$200
- 7) Total Compensation Per Participant for R61 = \$320. Participants may also choose to receive course extra credit as partial or total payment instead of cash (Research Experience Points) for their participation in this study (each ½ hour of assessment is worth 1 REP point).

Research Related Injury

There is no compensation for research related injury. The participant or the participants insurance company will be financially responsible for any injury occurring because of participating in this study.

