7.1 Specification of Safety Parameters

Participants will be asked about their health at the mid-study visit (Day 14) and final study visit (Day 28-32). Participants will be instructed to immediately inform the study team if any serious concerns arise with their health during the study.

The Side Effect Checklist (given at baseline, Week 1, Week 2, Week 3 and Week 4) will be used to assess NAC tolerability. If the side effect is marked as "1" (mild, does not interfere with functioning), nothing will be done. If the side effect is marked as "2" (moderate, some interference with functioning), or "3" (severe, functioning is significantly impaired because of side effects), and this rating denotes an elevation from baseline, and is considered to be at least possibly related to study intervention by the Principal Investigator and/or the Independent Clinical Monitor, we will discuss with participant (and, for adolescents under 18, the parent or guardian) to further assess the participant's impairment from the issue and make a joint decision about the risks versus benefits of staying at the same dose versus decreasing the dose. This determination will consider the frequency and the level of impairment associated with the side effect.

The PHQ-9, the BDI-II and the BSSI (given at baseline, Week 1, Week 2, Week 3 and Week 4) will all be used to assess suicide risk. If the participant indicates elevations in suicidal thinking (e.g. marks a “2” on the question about suicidal thinking on the BSSI) this will trigger a deeper safety assessment as described below.

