7.2 Methods and Timing for Assessing, Recording, and Analyzing Safety Parameters

The weekly assessment for side effects and suicide risk assessment is based on recommendations from the FDA’s 2004 recommendations that adolescents be seen weekly in the first month of antidepressant treatment to allow for suicide risk assessment.

The study team will review the results of the weekly questionnaires (side effect checklist, ISAS-SLV, PHQ-9) on a weekly basis. In addition, if the participant responded a “2” to any of the following questions on the BSSI: 9, 12, 13, 15, or 16 (these responses correspond to the statements “I cannot keep myself from committing suicide”, “I have a specific plan for killing myself”, “I have access or anticipate having access to the method that I would choose for killing myself and also have or shall have the opportunity to use it”, “I am sure that I shall make a suicide attempt”, and “I have almost finished or completed my preparations for committing suicide,” respectively), this will immediately trigger an automatic email to the study team with the item response and the participant ID, alerting them to contact the participant as soon as possible to assess safety and engage in safety planning. Similarly, if the participant responded a “3” to any question on the side effects checklist, the study team will receive an email prompting them to contact the participant as soon as possible.

The study team will follow up with all participants who rated side effect items as a “moderate” or “severe” to further assess the impact that these issues are having on their functioning. The study team will also follow up with participants or who spontaneously raised concerns about their health. Side effects or other health changes that are confirmed by the research team to be significantly impacting functioning (e.g. interfering with school, work, requiring treatment) will be labeled as adverse events (AEs). All adverse events will be reviewed by the Independent Clinical Monitor who will assist the PI in determining relatedness, whether the AE constitutes an Unexpected Problem (see below) and what corrective measures should be taken (e.g. decrease dose, discontinue treatment, withdraw participant.) The study team will log adverse effects including their timing, relatedness to the study drug, corrective measures taken, and resolution.

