Adverse Events, Unanticipated Problems and Serious Adverse Events will be recorded by study staff throughout the study occurring any time after informed consent is obtained until 7 (for non-serious AEs) or 30 days (for SAEs) after the last day of study participation. These will be recorded in an Excel document and kept on file in an electronic secure UMN Box folder for the study. There will be no identifying information recorded in this document and subjects will be identified by subject ID number (GRID number). In addition to whether AE was UP or SAE, details of event, and date of occurrence, we will also label organ system where it occurred (general, psychiatric, nervous system, etc.), severity, expectedness, relationship to study, if it was reported and date of reporting if so, day of trial it occurred (i.e. 1-32), if resolution/stabilization occurred and date of resolution/stabilization. All adverse events will be reviewed with the assigned Independent Clinical Monitor to assist in characterizing the adverse event (e.g. relatedness to study drug, determining if it should be classified as an Unexpected Problem), whether the new information warrants a change to the protocol or consent form (e.g. description of risks) and whether a dose change or participant withdrawal is indicated.

At each study visit (Days 1, 14, and 28 - 32) study staff will inquire about the occurrence of AE/SAEs since the last visit. If AE is ongoing and resolution of AE

has not occurred at time of reporting by subject, study staff will assess resolution/stabilization 1 week later via phone contact. Study staff will cease to assess previous AE of a participant 2 weeks after last day of study participation by that participant.

Safety review by Independent Monitoring Committee will occur if resolution of AE has not occurred 2 weeks after discontinuing study drug (due to study completion or dropout) and AE is considered to be related to study intervention (possibly, probably or definitely) by study PI.

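### When Visit 4 is moved past Day 32, study drug can be extended to Day 35 with no safety check attached, 10 to 16 days after the Day 21 survey

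*Combined protocol and SAP*

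**What the plan says.** Section 7.1 sets the rhythm of safety checks: "The Side Effect Checklist (given at baseline, Week 1, Week 2, Week 3 and Week 4) will be used to assess NAC tolerability". It gives the same timing for the suicide-risk questionnaires. Section 7.2 explains why: "The weekly assessment for side effects and suicide risk assessment is based on recommendations" that adolescents be seen weekly in the first month of antidepressant treatment.

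The checks for Weeks 1 to 3 are listed in Section 6.2.4, each with a window of two days either side. The last of them is headed "Day 21 (+/- 2 days) Assessments/Activities" and consists of the PHQ-9, the ISAS-SLV, the Side Effect Checklist and a medication-change form. The Week 4 measures are listed only under Visit 4 in Section 6.2.5, with a window of Day 28-32. The schedule in Section 6.1 heads that column Day 28.

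Section 5.1 dispenses four weeks of drug plus four spare days. Section 6.2.5 then adds: "If the participant unexpectedly needs to have their final visit rescheduled", staff will prescribe a further small supply "to allow the participant to continue taking study medication up until the final visit, to a maximum of 35 days".

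The other contacts fall outside the gap. Section 7.3 says: "At each study visit (Days 1, 14, and 28 - 32) study staff will inquire about the occurrence of AE/SAEs since the last visit". Section 5.1 has a contact on Day 3, 4 or 5. The closing phone call in Section 6.2.5 comes 24-72 hours after the final dose.

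**The concern.** The Week 4 check has no fallback if Visit 4 is late. Rescheduling past Day 32 does two things at once: it postpones the check and it lengthens exposure. The provision covers only the second.

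Section 7 describes these participants as more likely than others to attempt suicide. Under Sections 7.1 and 7.2, moderate or severe side-effect ratings and rises in suicidal thinking prompt follow-up and, for side effects, a decision about dose. If the check is late, those actions are late too, while capsules are still being taken. Until Visit 4, detection depends on the participant volunteering the problem.

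**Working it through.** The documents state no maximum interval between checks, so there is no figure to reproduce. The check is calendar arithmetic.

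**Inputs**
- Day 7 set: Day 5-9. Day 14 visit: Day 12-16. Day 21 set: Day 19-23 (Section 6.2.4).
- Visit 4: Day 28-32, extendable to Day 35 (Section 6.2.5). A maximum of 35 days is read as Day 35, because dosing starts on Day 1.
- Initial supply: 28 + 4 = 32 days (Section 5.1), so drug beyond Day 32 needs a new prescription.

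Table 1 in Section 3 still shows Visit 4 as Day 28 +/- 3. I use Day 28-32, which Section 6.2.5 gives and which matches the supply.

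**Formula.** Longest interval = latest day of the later check minus earliest day of the earlier check. The shortest is the reverse. Days with no check in between are one fewer than the interval.

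**Earlier weekly checks**
- Day 7 to Day 14: 16 - 5 = 11 at most.
- Day 14 to Day 21: 23 - 12 = 11 at most.

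**Day 21 set to Visit 4**

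| Visit 4 on | Shortest | Survey on Day 21 | Longest |
|---|---|---|---|
| Day 28 | 28 - 23 = 5 | 7 | 28 - 19 = 9 |
| Day 30 | 30 - 23 = 7 | 9 | 30 - 19 = 11 |
| Day 31 | 31 - 23 = 8 | 10 | 31 - 19 = 12 |
| Day 32 | 32 - 23 = 9 | 11 | 32 - 19 = 13 |
| Day 33 | 33 - 23 = 10 | 12 | 33 - 19 = 14 |
| Day 34 | 34 - 23 = 11 | 13 | 34 - 19 = 15 |
| Day 35 | 35 - 23 = 12 | 14 | 35 - 19 = 16 |

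**Counting permitted date pairs**
- Normal window, 5 survey days x 5 visit days = 25. Three exceed 11 days: Day 19 to 31 (12), Day 19 to 32 (13) and Day 20 to 32 (12).
- Day 33-35, 5 x 3 = 15. Those above 11 days number 3 at Day 33, 4 at Day 34 and 5 at Day 35, so 12 of 15. Those above 13 days, the normal-window maximum, number 1 + 2 + 3 = 6 of 15.

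**With a check by Day 32 before extra drug is prescribed**
- Survey to check: at most 32 - 19 = 13.
- Check to a Day 35 visit: 35 - 32 = 3 if taken on Day 32, and 35 - 28 = 7 if taken on Day 28. This leg stays within 13 days as long as the forms are taken on or after Day 22 (35 - 22 = 13).

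**Review lag.** Section 7.2 says: "The study team will review the results of the weekly questionnaires (side effect checklist, ISAS-SLV, PHQ-9) on a weekly basis". Under that routine a form completed on Day 32 might be read as late as Day 39 (32 + 7), after the last possible dose.

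**The case against.** The case for leaving the plan alone has real content.

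- **A reader might infer that the Week 4 check has no date.** It has one: the schedule puts Visit 4 at Day 28, and Section 6.2.5 bounds it at Day 28-32. The Week 2 check is tied to a visit in the same way. What is missing is a fallback when the visit is late.
- **A reader might infer that the normal window is itself at fault.** It is not, to any degree worth acting on. The excess over 11 days is one or two days, in 3 of 25 date pairs, and only if the survey is done on Day 19 or 20. With the survey on Day 21, no visit on Day 28-32 exceeds 11 days.
- **Eleven days is not a limit set by the plan.** It is the worst case of the two-day windows, used here only for comparison.
- **The weekly rationale covers the first month.** Days 33-35 lie beyond it, after three scheduled sets on a dose that is never escalated.
- **Other safeguards exist.** Section 7.1 says: "Participants will be instructed to immediately inform the study team if any serious concerns arise with their health during the study". Extra drug cannot be prescribed without contact. Supplement IV covers safety concerns that arise remotely.

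All of this stands and limits the weight of the point. None of it supplies a check when drug is extended. Reporting by the participant is not a scheduled assessment, and the rescheduling contact has no safety content specified.

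**Conclusion.** The point holds for the extension beyond Day 32, as a minor but worthwhile safety correction. In that case the plan lengthens exposure in a population it regards as at risk, with no check attached, and the interval since the Day 21 survey reaches 10-16 days.

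The 16-day figure needs both the earliest survey and the latest visit. The counts are of permitted dates, not probabilities, and the documents give no frequency of late visits. The intervals assume that the Day 21 set is completed in its window. They also assume that the rescheduling contact includes no unwritten safety questions.

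It would go too far to conclude that weekly monitoring is abandoned: Weeks 1 to 3 are scheduled, and a visit on Day 28-32 delivers the Week 4 check.

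**What to change.** In Section 6.2.5, make a safety check a condition of prescribing study drug beyond Day 32:

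- Obtain the existing PHQ-9 and Side Effect Checklist, online or by phone on the rescheduling call, no later than Day 32. If that call comes before Day 22, take the forms later, still by Day 32.
- Review the responses on receipt rather than at the next weekly review.
- Follow up under Sections 7.1 and 7.2 and Supplement IV. Section 7.2 alone is not enough, because its specified triggers are BSSI items and side-effect ratings and it sets none for the PHQ-9.
- Record these forms as safety checks only. Keep them out of the between-group tolerability comparison in Section 9.6, since only some participants will have them, and out of the 28/35 adherence count in Section 5.4.
- Do not add the ISAS-SLV, so that its recall period at Visit 4 is unchanged.

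The cost is two short forms and prompt staff review for those whose final visit moves past Day 32, plus the protocol wording; no extra visit is needed. One limitation remains: these forms do not include the BSSI, so its automatic email alert does not apply and suicide risk rests on prompt reading of the PHQ-9.

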7. SAFETY ASSESSMENTS

Safety will be monitored throughout the study. Here we review the risks associated with the study and how we will monitor for these risks.

1. Monitoring for safety related to taking NAC: Side effect reports in published studies of oral NAC have ranged from 81% reporting no side effects (N=1,392)(Tattersall, Bridgman, and Huitson 1983) to no significant between group differences in adverse events (N=75)(Berk et al. 2008). Oral NAC may cause gastrointestinal adverse effects including nausea, stomach discomfort,

diarrhea, and constipation, as well as headache, chest tightness, rash and/or itching. (Behr et al. 1997; Oldemeyer et al. 2003). These problems were reported as resolved following discontinuation of NAC. Adverse effects due to NAC will be monitored using the Side Effects Checklist. Participants who experience adverse effects which are bothersome and which are deemed likely or probably related to study drug will be instructed to decrease their dose by 1 capsule daily until they tolerate the study drug.

2. **Monitoring for safety related to IV catheter placement and blood collection:** The risks of the IV catheter and blood collection include pain at the site, bleeding, bruising, fainting and/or dizziness, superficial phlebitis and infection. These risks will be lessened by using trained technicians to perform this procedure. These potential adverse effects would be acute and reversible.
3. **Monitoring for safety related to suicide risk:** Our study population is at increased risk for suicide attempts (Horwitz, Czyz, and King 2015; Tang et al. 2011; Victor and Klonsky 2014). Suicide risk will be monitored throughout the study in the form of questionnaires and interviews. If a concern for imminent suicide risk is identified, the study team will conduct a more in-depth safety assessment and will engage the adolescent in safety planning. As indicated, this safety assessment and planning may include the parent(s), other family members, treatment team, and / or referral for emergency services / hospitalization. Refer to Supplement IV: RAD Lab procedure on suicide and self-harm behavior risk.
4. **Monitoring for safety related to clinical assessment:** Some of the questions that participants will be asked may make them feel uncomfortable or upset. These pertain to psychiatric and medical history, behavioral and psychiatric symptomatology. Participants are informed that they do not have to answer any question that makes them feel uncomfortable. Clinicians interviewing the participants will remind them of this, as well as use empathy to gauge their discomfort. Staff will be sufficiently trained to handle these situations. If participants are not able to share enough critical information needed for the study (e.g. inclusion and exclusion criteria, NSSI etc.) the participant will be withdrawn.
5. **Monitoring for safety related to MRI scanning:** The MRI scanning device will be a 7.0 Tesla MRI scanner. This device has been evaluated by the FDA as having non-significant risk for persons more than one month of age and data already reviewed by the UMN IRB indicate that the 7.0 Tesla magnetic field does not pose a significant risk to human volunteers. All participants will be screened according to CMRR policies to minimize risks to participants. If participants are not able to tolerate the scanning session, it will stop and they will exit the study. These are the specific risks related to MRI scanning:
 - a) **Exposure to high magnetic field:** The primary known hazard associated with exposure to a static high magnetic field is that the magnet exerts a strong force on ferromagnetic objects. Metallic objects that are entered the magnetic field can accelerate into the magnet potentially causing damage

to the magnet or persons in the magnet room. In addition, implanted metallic objects can be displaced. MRI may not be appropriate in the presence of the following conditions: cardiac pacemaker; metal fragments in eye, skin, body; mechanical heart valve replacement; brain clips; venous umbrella; being a sheet-metal worker or welder; aneurysm surgery; intracranial bypass; renal, aortic clips; middle ear, eye, joint, or penile implants; joint replacements; hearing aid; neurostimulator; insulin pump; intra-uterine device (IUD); shunts/stents anywhere in the body; metal mesh/coil implants; metal plate/pin/screws/wires anywhere in the body, any other metal implants; permanent eyeliner or permanent artificial eyebrows. All participants will be initially screened first via the online screen before enrollment, then using the CMRR Safety Screening Form at the day of MR scanning. The CMRR Safety Screening Form will not be submitted, as further updates are rolled out by the Center for Magnetic Resonance Research. The study will use the published version of the form on the website (<https://www.cmrr.umn.edu/policies/>). Participants that do not pass screening will not enter the CMRR where magnetic fields exist.

- b) Radiofrequency pulses impart small amounts of energy into the participant. No ionizing radiation is used with MRI. Because the pulse sequences to be used fall within FDA guidelines and will not be operated outside of safe limits, we do not expect any hazard associated with power deposition. To prevent inadvertent application of significant energies which may result in heating, the scanning systems include monitoring with both a hardware and a software monitor. Participants will be instructed to report any heating sensation immediately, and that the scan could be stopped at any time if this occurs.
- c) Peripheral nerve stimulation from rapidly switching magnetic fields (dB/dt) during the scanning procedure may occur. As a result, the participant may experience muscle twitching or tingling sensations lasting seconds to minutes. This is considered to occur seldomly. Participants are instructed that if twitches do occur, they should immediately inform the operator. This would be a short-lived side effect and reversible.
- d) Acoustic noise: MR imaging creates acoustic noise because of pulsing currents through the gradient coils within the magnetic field. A repetitive tapping sound occurs as a result. Ear plugs are provided to the participant to prevent hearing damage and provide comfort
- e) Claustrophobia: Some people undergoing this procedure become anxious and afraid when in closed spaces. Participants will be instructed that they can stop procedure at any time. The MRI technologist will be in communication with the participant during the scan and ask them how they are doing. In addition, participants will be given a squeeze ball to communicate an urgent need or concern. Participants are screened for claustrophobia before enrollment.
- f) Anatomical abnormalities revealed: There is a possibility that the MRI

scan would reveal unknown and unlooked for abnormalities such as a cyst, vascular abnormality or a tumor. The scan results will be routinely sent to a radiologist for review. If an abnormality is uncovered, the participants are informed of the results of the radiology review and are encouraged to follow up with their physician. We would provide participants physicians with a copy of the imaging data that we collect upon request.

- g) Dizziness and nausea: Dizziness and nausea are rare though may occur if the participants head moves around while they are inside the magnet. If this occurs, this would be acute and reversible, and should resolve within a few minutes without intervention.
- 6. Participants under the age of 18 will provide assent along with parental consent. The potential benefit for those engaging in NSSI, aged 16-24, from the insight gained because of this study outweighs the risks of this study. Risk is minimized by using dosages of NAC determined to be safe from previous research. Study procedures are minimal risk, and staff will be appropriately trained for all study procedures. Checklist HRP-416 is provided.
- 7. Email Risks: Participants will be able to opt in to communicating with study staff via unencrypted email to arrange their appointments and receive study instructions. There are risks associated with email communication, and these risks increase when the emails are sent without an encryption service. Risks of sending or receiving emails without encryption include, but are not limited to:
 - a) Others can intercept messages
 - b) If messages are sent or received on an employer-owned device, the employer may have the right to save and read the messages. The internet or cell-phone provider may also have the right to save and read email messages.
 - c) A copy of the message may be saved on a device or computer system, even if it is deleted.
 - d) If an email address is not typed correctly, it can be sent to the wrong person
 - e) Emails can spread computer viruses.
 - f) Others may be able to access messages on devices that were lost, stolen, or thrown away. If a user changes emails without notifying study staff, they may miss communications.
- 8. Text communication Risks: Participants may opt in to communicating with study staff via texting a University-owned cell phone to arrange study appointments and receive other study updates. There are risks associated with text communication, including but not limited to:
 - a) Others can intercept messages
 - b) If messages are sent or received on an employer-owned device, the employer may have the right to save and read the messages. The internet or

cell-phone provider may also have the right to save and read messages.

- c) A copy of the message may be saved on a device, even if it is deleted
- d) If the phone number is not typed correctly, it may be sent to the wrong person
- e) Others may be able to access messages on devices that were lost, stolen, or thrown away
- f) If a user changes phone numbers without notifying study staff, they may miss communications.

Participants will be notified that the phone will only be monitored during business hours (Mon-Fri 9AM-5PM), unless they have an appointment scheduled outside of those hours. They will be informed that they should not use this phone as an emergency contact number as well. Texts that are sent to the study phone will be regularly deleted, unless they are found to be significant to the participant's study record or safety. In this case, screen shots of the texts may be saved, sent to the study email address, and redacted to protect privacy. Please refer to Section 18.0 Confidentiality for redaction procedures. Study staff will not store the participant's name in the phone's contact book. Their number will be saved with their study ID code so study staff may identify them during conversations; once the participant completes participation in the study, their contact will be deleted.

Participants do not have to opt in to text communication in this study. If they change their mind about communicating via text, they can notify staff at any time about their communication preferences. If the participant would like to start using text during the study, they will need to sign a text communication consent form, discussed in Section 11.2 Informed Consent Forms.

